#### 4.4.2 Secondary Efficacy Variables

Secondary efficacy variables are defined in Section 4.5

#### 4.4.3 Handling of Missing Values/Censoring/Discontinuations

Missing data will not be replaced or imputed. Subjects who withdraw from the study prematurely will be included in the statistical analyses up to the point of discontinuation.

### 4.5 Analysis of Secondary Objectives

#### 4.5.1 Efficacy (Secondary)

##### The change from baseline in tactile threshold at Week 8

The change from baseline in tactile threshold at Week 8 is the secondary efficacy endpoint.

The null hypothesis for the secondary endpoint is that the mean change from baseline in tactile threshold is equal between the 2 products.

$$H_0: \mu_1 = \mu_2$$

The alternative hypothesis is that the mean change from baseline in tactile threshold score is not equal between the 2 products.

$$H_1: \mu_1 \neq \mu_2$$

This secondary efficacy variable analysis will be conducted for the following treatment comparison:

Test Product versus Negative Control at Week 8.

All other treatment comparisons based on the tactile threshold are part of the exploratory objectives.

---

The subjects tactile threshold will be derived as the average score of the 2 test teeth at each visit assessed and the change from baseline will be derived from the individual teeth first before calculating the average change of the 2 test teeth. If tactile threshold for test teeth is reported as “> 80g” at the post baseline assessments, the value will be taken as as 90g in the derivations.

Summary statistics of the observed mean tactile threshold scores and changes from baseline will be presented by treatment at Baseline, Week 4 and Week 8 (Table 14.2.2.1).

The change from baseline in tactile threshold at Week 8 will be calculated as the subject level mean change from baseline (on the 2 test teeth) and analyzed at Week 8 using ANCOVA with treatment and baseline Schiff stratification value as factors and baseline tactile threshold included as a covariate. Adjusted means of all treatments and their SEs, P-value and 95% CIs will be presented. Treatment differences and SE of all pairs of treatments will be provided together with P-values and 95% CIs (Table 14.2.2.2).

To visually inspect the treatment effect on tactile threshold scores, a plot across time, with the raw means together with SE bars will be produced. The plot will display a different symbol line for each treatment group (Figure 14.2.2).

The assumption of normality and homogeneity of variance in the ANCOVA model will be investigated and if violated, data transformations will be investigated. If suitable transformations cannot be found, non-parametric Van Elteren tests will be performed adjusting for the maximum baseline Schiff sensitivity scores and results will be compared with the ANCOVA results. If the inferences from the 2 analyses are similar then both sets of results will be reported and emphasis will be made on the ANCOVA results. In case of discrepancies between p-values of ANCOVA and van Elteren analysis, inferences will be drawn on the non-parametric analysis.

#### **4.5.2 Pharmacokinetic (Secondary)**

Not Applicable

#### **4.6 Analysis of Exploratory Objectives**

Exploratory analysis based on the exploratory efficacy variable change from baseline in Schiff sensitivity score and change from baseline in tactile threshold to post baseline (week 4 and 8) will be summarized, analyzed and presented as detailed for the primary and secondary endpoint respectively. Analysis assumptions will be investigated as detailed for the secondary efficacy analysis (Section 4.4.1 and 4.5.1).

The analysis will be conducted for exploratory efficacy variable of Schiff sensitivity scores and tactile threshold for below comparison (Table 14.2.1.2 and Table 14.2.2.2).

- Test Product versus Negative Control at Week 4
- Test Product versus Positive Control at Week 4 and 8
- Negative Control versus Positive Control at Week 4 and 8

---

All data for each efficacy variable will be presented for each subject at Baseline, Week 4 and Week 8 ([Listing 16.2.6.1](#) and [Listing 16.2.6.2](#)).

## 4.7 Analysis of Safety

### 4.7.1 Adverse Events and Serious Adverse Events

All safety data will be reported for the Safety Population as per actual treatment received. The safety profile of the study treatments will be assessed with respect to AEs. Oral soft tissue (OST) abnormalities are included as AEs if they appear or worsen after the initial assessment.

All AEs will be reviewed by the Clinical Research Scientist or Designee prior to database freeze and will be coded using the Medical Dictionary for Regulatory Activities (MedDRA). During this review stage, AEs will be further categorized as oral or non-oral.

AEs will be regarded as treatment-emergent if they occur on or after the first treatment application at the baseline visit.; if this date is missing a suitable alternative will be used eg date of randomization). All other AEs prior to this will be considered non-treatment emergent.

The following summary tables and listings will be presented by treatment group.

- Table of treatment-emergent AEs by system organ class (SOC) and Preferred Term (PT) ([Table 14.3.1.1](#))
- Table of treatment-emergent AEs by Oral/Non-Oral and PT ([Table 14.3.1.2](#))
- Table of treatment-emergent treatment-related AEs by SOC and PT ([Table 14.3.1.3](#))
- Table of treatment-emergent treatment-related serious adverse events (SAEs) by SOC and PT ([Table 14.3.1.5](#)) [only produced if there are more than 5 SAEs]
- Table of treatment-emergent treatment-related Non-serious SAEs by SOC and PT ([Table 14.3.1.6](#)) [only produced if there are more than 5 SAEs]
- Table of treatment-emergent treatment-related AEs by Oral/Non-Oral and PT ([Table 14.3.1.4](#))
- Listing of all AEs ([Listing 16.2.7.1](#) for all randomized subjects; [Listing 16.2.7.2](#) for non-randomized subjects)
- Listing of deaths ([Listing 14.3.2.1](#))
- Listing of non-fatal SAEs ([Listing 14.3.2.2](#))
- Listing of treatment-emergent AEs leading to study or drug withdrawal ([Listing 14.3.2.3](#))
- Listing of treatment-emergent AEs classified as oral ([Listing 14.3.2.4](#))
- Listing of OST abnormalities ([Listing 14.3.2.5](#))
- Listing of OHT abnormalities ([Listing 14.3.2.6](#))

In the event that there is nothing to report, a null listing will be produced.

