#### 10.2.5 Safety Analyses

Safety population will be used for safety assessments. Safety analyses will be performed according to the treatment that the subject received (using variable ATRT). All AEs will be reviewed by the Clinical Research Scientist or Designee prior to database lock and unblinding and will be coded using the Medical Dictionary for Regulatory Activities (MedDRA). During this review stage, AEs will be further categorized as oral or non-oral. AEs will be listed and summarized by treatment received. Serious AEs will also be listed. AEs will be regarded as treatment emergent if they occur on or after the first treatment application at the baseline visit. The following AEs tables split by treatment will be produced:

- Listing of all AEs (including Non-treatment emergent AEs from all subjects)
- Listing of all AEs for screened subjects
- Treatment emergent AEs by Oral/Non-Oral Preferred Term (PT)
- Treatment emergent AEs by System Organ Class (SOC) and PT
- Treatment emergent AEs by SOC, PT and intensity
- Treatment emergent treatment related AEs by Oral/Non-Oral
- Treatment emergent treatment related AEs by SOC and PT
- Listing of SAEs (if there are none a null listing will be produced; if there are more than 5 treatment emergent serious SAEs a table will be produced instead by SOC and PT)
- Non-serious treatment emergent AEs by SOC and PT (only produced if there are more than 5 SAEs)

OST abnormalities will be listed and tabulated. The tabulation will show changes in abnormality from baseline to each follow-up assessment.

Exposure to study product will also be tabulated and listed by treatment group.

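### SAP 4.7.1 limits the SAE and non-serious AE tables to treatment-related events and mistitles one; Protocol 10.2.5 sets no such limit, and SAP Section 5 does not declare the change

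*SAP*

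**What the plan says.** Protocol 10.2.5 introduces its safety displays with "The following AEs tables split by treatment will be produced". For SAEs it plans a listing, with this condition: "if there are more than 5 treatment emergent serious SAEs a table will be produced instead by SOC and PT". For the remaining events it plans "Non-serious treatment emergent AEs by SOC and PT (only produced if there are more than 5 SAEs". Neither item mentions causality.

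SAP 4.7.1 has two tables in the same place. Table 14.3.1.5 is the "Table of treatment-emergent treatment-related serious adverse events (SAEs) by SOC and PT". Table 14.3.1.6 is the "Table of treatment-emergent treatment-related Non-serious SAEs by SOC and PT". Each carries the same condition: "only produced if there are more than 5 SAEs".

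SAP Section 5 records changes from the protocol. Against Protocol 10.2.5 it declares three: the table by intensity is dropped, OST abnormalities are listed and not tabulated, and exposure is listed and not tabulated. It says nothing about the SAE table or the non-serious AE table.

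**The concern.** All-cause counts by arm do not depend on the investigator's opinion of causality, which Protocol 8.4.2 describes as a clinical judgment. The protocol committed to two all-cause tables once SAEs become numerous enough to tabulate. A programmer who follows the SAP would produce different content in both.

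Three things go wrong together. The causality restriction removes SAEs judged unrelated from the only table that isolates SAEs, and removes unrelated events from the non-serious table. The title of Table 14.3.1.6 describes events that are both non-serious and serious, which is impossible as written. And the trigger counts every SAE while the tables hold only related ones, so the tables can be called for by events that they then leave out.

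Safety is a stated objective of the trial, and a departure from the protocol's safety displays should be either corrected or declared with a reason.

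**Working it through.** The plan gives no figure on this point, so the check is mainly a comparison of text, with one calculation of how often it would matter.

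**1. The two plans side by side**

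| | Protocol 10.2.5 | SAP 4.7.1 |
|---|---|---|
| SAE table, content | treatment-emergent SAEs, any causality | treatment-emergent SAEs, related only (14.3.1.5) |
| SAE table, trigger | more than 5 treatment-emergent SAEs | more than 5 SAEs |
| Non-serious table, content | non-serious treatment-emergent AEs, any causality | related only, titled as non-serious SAEs (14.3.1.6) |
| Non-serious table, trigger | more than 5 SAEs | more than 5 SAEs |
| Declared in SAP Section 5 | – | no |

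The protocol's silence on causality is not loose drafting. Two other items in the same list are expressly confined to treatment-related events, so where the protocol wants that restriction it states it.

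**2. Does another SAP table fill the gap?**

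- Table 14.3.1.1 ("Table of treatment-emergent AEs by system organ class (SOC) and Preferred Term (PT") and Table 14.3.1.2 (oral/non-oral) count all treatment-emergent AEs by arm, but do not separate serious from non-serious.
- Tables 14.3.1.3 and 14.3.1.4 cover related AEs only.

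So no SAP summary table isolates all-cause SAEs, or all-cause non-serious events, by arm. If the title of 14.3.1.6 is read as non-serious AEs, Tables 14.3.1.5 and 14.3.1.6 merely split Table 14.3.1.3 by seriousness.

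**3. Trigger against content: a worked case**

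Suppose 6 treatment-emergent SAEs occur and all are judged unrelated. Since 6 > 5, both triggers are met under either document.

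- Protocol: the SAE table shows 6 events; the second table shows all non-serious treatment-emergent AEs.
- SAP Table 14.3.1.5: 0 events.
- SAP Table 14.3.1.6: 0 events if read literally; if read as non-serious AEs, the related non-serious AEs, which may be any number.
- SAP Table 14.3.1.1: the 6 SAEs are counted, mixed with the non-serious events.

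Protocol 8.2.2 collects SAEs of any causality from consent onward. The SAP trigger can therefore count events that are unrelated, not treatment-emergent, or both.

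**4. How likely is the trigger?**

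The documents give no SAE rate, so a range is assumed. Take n = 180 randomized subjects (Protocol 10.1), at most one SAE each, occurring independently with probability p. The chance of more than 5 SAEs is

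P(X ≥ 6) = 1 − Σ (k = 0 to 5) C(180, k) p^k (1 − p)^(180 − k).

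| Assumed p | Expected SAEs (180 × p) | P(6 or more) |
|---|---|---|
| 0.5% | 0.9 | 0.03% |
| 1% | 1.8 | 1.0% |
| 2% | 3.6 | 15% |
| 3% | 5.4 | 45% |
| 5% | 9.0 | 89% |

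SAEs in screened subjects who are not randomized, or several SAEs in one subject, would raise the count somewhat.

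**The case against.** The strongest reply is that little information is lost. Tables 14.3.1.1 and 14.3.1.2 are unconditional, by arm, and restricted by neither causality nor seriousness, so every unrelated treatment-emergent SAE and every non-serious treatment-emergent AE is counted there. The SAP also keeps its "Listing of deaths" (14.3.2.1) and its listing of non-fatal SAEs (14.3.2.2) whatever the count or causality, and Listing 16.2.7.1 shows seriousness and relatedness for each event. With 180/3 = 60 subjects per arm, SAEs can be counted by hand. The protocol itself offers only a listing at 5 SAEs or fewer. All of this stands, and it limits the point.

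A reader might infer that the SAP leaves unrelated SAEs in listings only, or never tabulates all-cause events. The documents do not support that: the events are tabulated, but pooled. What is missing is a table that isolates them.

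A reader might also infer that Table 14.3.1.6 is empty by design. That is too literal. Its position and trigger match the protocol's non-serious AE table, and the protocol has a comparable slip of its own in writing of serious SAEs. A misprint is the likelier explanation. Correcting it does not remove the causality restriction, which appears in both table definitions.

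Finally, no shell for either table is shown, and the worksheet of data displays in Attachment 1 is not reproduced, so the titles used in programming cannot be checked. That is a fair limit; the SAP text still needs to be right.

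**Conclusion.** The point holds as an undeclared mismatch between the SAP and the protocol in two conditional tables. Following the SAP as written gives the wrong content in both once the trigger is met: all-cause SAEs and all-cause non-serious treatment-emergent AEs are not isolated by arm in any summary table, and the trigger does not match what the tables contain.

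The materiality is low. Nothing differs in these tables unless there are more than 5 SAEs, which is unlikely if the SAE rate is 1% or less and becomes a real possibility at 2% to 3%. Those rates are assumptions. Above the trigger, the same events remain in the pooled tables and SAEs remain in unrestricted listings by arm. No efficacy conclusion is affected.

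**What to change.** In SAP 4.7.1:

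- Delete the treatment-related restriction from the definitions of Tables 14.3.1.5 and 14.3.1.6.
- Retitle Table 14.3.1.6 as non-serious treatment-emergent AEs by SOC and PT.
- Use the protocol's triggers: more than 5 treatment-emergent SAEs for Table 14.3.1.5 (the SAP now omits treatment-emergent there), and more than 5 SAEs for Table 14.3.1.6 (already so). A single trigger for both would be tidier, but it departs from the protocol and should then be declared in SAP Section 5.
- Keep Listings 14.3.2.1, 14.3.2.2 and 16.2.7.1 as they are.
- Check that Attachment 1 and the table shells carry the same titles.

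If the restriction to related events was intended, state it in Section 5 with a reason.

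The cost is two lines of SAP text and two table titles. No extra data are needed.

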#### 4.8 Analysis of Other Variables

To cover the Chinese Ministry of Health guideline requirement, to demonstrate at least a 15% difference between the Test Product and Negative Control, the difference between treatments in the raw means of the actual score (note: not change from baseline) will be calculated using below formula for Schiff sensitivity and tactile threshold at Weeks 4 and 8 (Table 14.2.1.1 and 14.2.2.1).

$$100 * (\text{Test Product} - \text{Negative Control Product}) / \text{Negative Control Product}$$

Similar difference will be calculated between Test product and Positive Control.

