d) Minimum of two, non-adjacent accessible teeth (incisors, canines, pre-molars), with signs of sensitivity, measured by response to a qualifying tactile stimulus (Yeaple ≤20g) and evaporative air assessment (Schiff sensitivity score ≥2). The two selected test teeth must have also qualified at Screening for this criteria.

**Note:** The Investigator will select two *Test Teeth* from those which meet *both* the tactile threshold and Schiff sensitivity score criteria, in addition to meeting all other criteria. *Test Teeth* should not be adjacent to each other and preferably in different quadrants.

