#### 10.2.10 Other Analyses

To cover the Chinese requirement to demonstrate a 15% difference between the Test Product and Control product 1, the difference between treatments in the raw means of the actual score (note not change from baseline) will be calculated and presented. This will be done for Schiff and tactile at weeks 4 and 8. The calculation is: -

100\*(Test-Ref 1)/Ref 1

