### 5 Changes to the Protocol Defined Statistical Analysis Plan

Changes from the originally planned statistical analysis specified in the protocol are outlined in below table

Protocol	Reporting & Analysis Plan	
Statistical Analysis section	Statistical Analysis Plan	Rationale for Changes

10.2.6. Definition of Analysis Populations
 
 
The ITT population includes all randomized subjects who receive at least one dose of investigational product and analysed as randomized.
 
The PP population includes all subjects who fully comply with all study procedures and restrictions and is a sub-set of the ITT population. Any protocol deviations that would lead to subjects/data being excluded will be removed from the PP
 
	
4.1.3 Analysis Population
 
 
 Comprise of all randomized subjects who receive at least one dose of study treatment and have at least one post-baseline efficacy evaluation. This population will be based on the treatment to which the subject was randomized.
 
 All subjects who are assessed as sufficiently compliant with study procedures and restrictions.
 
 Subjects with major protocol deviations will be excluded. Depending on the nature of the
 
	
To keep consistency across oral studies and to differentiate from ITT population definition from safety population.

Protocol	Reporting & Analysis Plan	
Statistical Analysis section	Statistical Analysis Plan	Rationale for Changes
population.	major protocol deviation and impact on the efficacy variable (s), subjects will be either completely excluded from PP population or only partially excluded from the PP analyses. This will be determined on a case-by-case basis.	

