
Protocol 208153

Program Run Date:xxxx

Table 14.2.1.1  
Summary Statistics of Evaporative (Air) Schiff Sensitivity Score  
Intent-to-Treat Population

Study Population: Intent to Treat (N=XXX)

Visit		Test Product (N=XX)		Negative Control (N=XX)		Positive Control (N=XX)		Overall
		Observed Value	Change from Baseline	Observed Value	Change from Baseline	Observed Value	Change from Baseline	Observed Value
BASELINE	n	XX		XX		XX		XX
	n (Missing)	XX		XX		XX		XX
	MEAN	X.XX		X.XX		X.XX		X.XX
	SE	X.XX		X.XX		X.XX		X.XXX
	SD	X.XXX		X.XXX		X.XXX		X.XXX
	MEDIAN	X.X		X.X		X.X		X.XX
	MINIMUM	X.X		X.X		X.X		X.XX
	MAXIMUM	X.X		X.X		X.X		X.X
WEEK 4	n	XX	XX	XX	XX	XX	XX	
	n (Missing)	XX		XX		XX		XX
	MEAN	X.XX	X.XX	X.XX	X.XX	X.XX	X.XX	
	SE	X.XX	X.XX	X.XX	X.XX	X.XX	X.XX	
	SD	X.XXX	X.XXX	X.XXX	X.XXX	X.XXX	X.XXX	
	MEDIAN	X.X	X.X	X.X	X.X	X.X	X.X	
	MINIMUM	X.X	X.X	X.X	X.X	X.X	X.X	
	MAXIMUM	X.X	X.X	X.X	X.X	X.X	X.X	

Stannous Fluoride (SnF2)

208153

Final Statistical Reporting and Analysis plan V1.0 14 Dec 2017

---

Visit	Test Product (N=XX)		Negative Control (N=XX)		Positive Control (N=XX)		Overall
	Observed Value	Change from Baseline	Observed Value	Change from Baseline	Observed Value	Change from Baseline	Observed Value
WEEK 8	SAME AS WEEK 4.						

---

Stannous Fluoride (SnF2)

208153

Final Statistical Reporting and Analysis plan V1.0 14 Dec 2017

Protocol 208153

Program Run Date:xxxx

Table 14.2.1.2  
Statistical Analysis of Change from Baseline in Evaporative (Air) Schiff Sensitivity Score  
Intent-to-Treat Population

Study Population: Intent to Treat (N=XXX)

	Test Product (N=XX)	Negative Control (N=XX)	Positive Control (N=XX)		
WEEK 4					
ADJUSTED MEAN [1]	XX.XX	XX.XX	XX.XX		
SE [1]	XX.XXX	XX.XXX	XX.XXX		
95% CI [1]	(XX.XXX, XX.XXX)	(XX.XXX, XX.XXX)	(XX.XXX, XX.XXX)		
P-VALUE [1]	0.XXXX	0.XXXX	0.XXXX		
COMPARISONS BETWEEN TREATMENTS	DIFFERENCE (SE) [1]	95% CI [1]	P-VALUE [1]	MEAN DIFFERENCE % [2]	.
TEST PRODUCT VERSUS NEGATIVE CONTROL [1] *	XX.XX (XX.XXX)	(XX.XXX, XX.XXX)	0.XXX	xx.xx	
TEST PRODUCT VERSUS POSITIVE CONTROL [1]	XX.XX (XX.XXX)	(XX.XXX, XX.XXX)	0.XXX	XX.XX	
NEGATIVE CONTROL VERSUS POSITIVE CONTROL [1]	XX.XX (XX.XXX)	(XX.XXX, XX.XXX)	0.XXX		
WEEK 8 (AS ABOVE FOR WEEK 4)					
...					

\* Test Product versus Negative Control at Week 8 is a primary endpoint comparison.

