[1] From ANCOVA model with treatment as factor and baseline Schiff score as covariate. Difference is first named treatment minus second named treatment such that a negative difference favors the first named treatment.

[2] For the Chinese Ministry of Health guideline requirement to demonstrate difference between Test Product and Control (Positive or Negative) in the observed raw means. It is Calculated as  $100 * (\text{Test Product} - \text{Control}) / \text{Control}$ .

Page x of y

PPD

GlaxoSmithKline Consumer Healthcare Confidential

Stannous Fluoride (SnF2)

208153

Final Statistical Reporting and Analysis plan V1.0 14 Dec 2017

*Programming Note: For Table 14.2.2.2 and 14.2.2.4: please update footnote [1] as  
[1] From ANCOVA model with treatment and baseline Schiff stratification as factors and baseline tactile threshold as a covariate. Difference is the first named  
treatment minus second named treatment such that a positive difference favors the first named treatment.*

Stannous Fluoride (SnF2)

208153

Final Statistical Reporting and Analysis plan V1.0 14 Dec 2017

Protocol 208153

Program Run Date:xxxx

Table 14.3.1.1  
Treatment Emergent Adverse Event by SOC and Preferred Term  
Safety Population

Study Population: Safety Population (N=xx)

SOC Preferred Term	Test Product (N=XX)		Negative Control (N=XX)		Positive Control (N=XX)		Overall (N=XX)	
	n (%)	nAE	n (%)	nAE	n (%)	nAE	n (%)	nAE
NUMBER OF SUBJECTS WITH AT LEAST ONE AE	xx (xx.x)	xx	xx (xx.x)	xx	xx (xx.x)	xx	xx (xx.x)	xx
NUMBER OF SUBJECTS WITH NO AE	xx (xx.x)	xx	xx (xx.x)	xx	xx (xx.x)	xx	xx (xx.x)	xx
SKIN AND SUBCUTANEOUS TISSUE DISORDERS	xx (xx.x)	xx	xx (xx.x)	xx	xx (xx.x)	xx	xx (xx.x)	xx
ERYTHEMA	xx (xx.x)	xx	xx (xx.x)	xx	xx (xx.x)	xx	xx (xx.x)	xx
DERMATITIS	xx (xx.x)	xx	xx (xx.x)	xx	xx (xx.x)	xx	xx (xx.x)	xx
GASTROINTESTINAL SYSTEM	xx (xx.x)	xx	xx (xx.x)	xx	xx (xx.x)	xx	xx (xx.x)	xx
ABDOMINAL PAIN	xx (xx.x)	xx	xx (xx.x)	xx	xx (xx.x)	xx	xx (xx.x)	xx
DRY MOUTH	xx (xx.x)	xx	xx (xx.x)	xx	xx (xx.x)	xx	xx (xx.x)	xx
VOMITTING	xx (xx.x)	xx	xx (xx.x)	xx	xx (xx.x)	xx	xx (xx.x)	xx

Etc.

n (%) = Number (percent) of subjects nAE = Number of adverse events.

Page x of y

PPD

Stannous Fluoride (SnF2)

208153

Final Statistical Reporting and Analysis plan V1.0 14 Dec 2017

Protocol 208153

Program Run Date:xxxx

Listing 16.1.7  
Randomization Information  
Randomized Population

Study Population: Randomized (N=xx)  
Stratum 1: Maximum Schiff score =2

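### Do the SAP's mismatched table references and footnote for the 15% guideline percentage call for a change to the plan?

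*SAP*

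**What the plan says.** Protocol 10.2.10 opens the topic with "To cover the Chinese requirement to demonstrate a 15% difference between the Test Product and Control product 1". It asks for a percentage difference in raw means, not in change scores, for Schiff and tactile at Weeks 4 and 8, computed as 100 × (Test − Ref 1)/Ref 1. SAP 4.8 repeats this with the Negative Control as comparator and states that the figure "will be calculated using below formula for Schiff sensitivity and tactile threshold at Weeks 4 and 8 (Table 14.2.1.1 and 14.2.2.1". It then adds one line: "Similar difference will be calculated between Test product and Positive Control".

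The shells in SAP Appendix 1 differ from this in two ways.

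- **Place.** The Table 14.2.1.1 shell holds only counts and descriptive statistics. The percentage has its own column, "MEAN DIFFERENCE % [2", in the ANCOVA table, 14.2.1.2.
- **Label.** Footnote [2] to that column says the guideline requirement is "to demonstrate difference between Test Product and Control (Positive or Negative) in the observed raw means". It does not mention 15%.

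Footnote [1] of the same table says that a negative difference favours the first-named product. A programming note that begins "For Table 14.2.2.2 and 14.2.2.4: please update footnote [1] as" reverses this for tactile. Neither footnote [2] nor SAP 4.8 gives a favourable sign for the percentage itself.

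SAP Section 5 says "Changes from the originally planned statistical analysis specified in the protocol are outlined in below table". The Positive Control percentage is not in that table.

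**The concern.** Taken literally, the SAP gives two homes for one number and two descriptions of the requirement it serves. A programmer working from SAP 4.8 would look for the percentage in a table with no field for it. A reader of Table 14.2.1.2 could take the percentage against a marketed competitor as something the guideline demands, although SAP 4.8 and the protocol give the requirement for the Negative Control. A 15% difference without a stated sign could be misread, because benefit is negative on one scale and positive on the other.

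The point looks weightier because Protocol 1.2.1 justifies the trial by the need to meet the Ministry of Health guideline. Statistical significance and a 15% threshold can also disagree, and neither document says in so many words how the two relate. If the percentage fed a decision rule, an unclear comparator or sign would matter.

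**Working it through.** **1. The plan's own figure.** Inputs from Protocol 10.1 and SAP 1.4: difference 0.33, SD 0.619, 55 per arm, two-sided 5%.

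- Standard error = 0.619 × √(2/55) = 0.118.
- 0.33/0.118 = 2.80, and 2.80 − 1.96 = 0.84, so power is 79.8% by the normal approximation. The noncentral t gives 79.1%.
- The stated 80% reproduces. The guideline percentage does not enter this calculation.

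**2. Does the choice of table alter the number?**

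| Item | SAP 4.8 text | Table 14.2.1.2 shell |
|---|---|---|
| Formula | 100 × (Test − Control)/Control | the same |
| Quantity | raw means | raw means |
| Visits | Weeks 4 and 8 | Weeks 4 and 8 |
| Comparators | Negative; Positive added | Negative and Positive rows filled; Negative versus Positive left blank |
| Table and population | 14.2.1.1, ITT | 14.2.1.2, ITT |

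Every input matches. Table 14.2.1.1 also prints the observed mean for each arm at each visit, so the tables cited in SAP 4.8 do hold the means behind the percentage, and a reader can recompute it up to rounding. Only the Schiff shells are shown. The tactile layout is inferred from the programming note, which treats 14.2.2.2 as the same table with footnote [1] changed.

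**3. How many percentages, and how many carry the loose label?** 2 scales × 2 visits × 2 comparisons = 8, of which 2 × 2 = 4 are against the Positive Control. SAP 4.8 plans all eight, so the footnote neither adds nor removes any.

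**4. Can the favourable sign be recovered?** The control mean in the denominator is positive, so the percentage has the sign of Test minus Control. On the Schiff scale (Protocol 7.2.2.1) a higher score is a worse response, so negative is benefit. The tactile threshold (Protocol 7.2.1) is the force that elicits pain, so positive is benefit. Examples with assumed control means, which the documents do not give:

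- Schiff, control 2.0, test 1.67: 100 × (1.67 − 2.0)/2.0 = −16.5%.
- Tactile, control 40 g, test 46 g: 100 × (46 − 40)/40 = +15%.

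These signs agree with footnote [1] and with its tactile version.

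**5. Can significance and 15% disagree?** Yes. The smallest significant Schiff difference at 55 per arm is 1.982 × 0.619 × √(2/55) = 0.234. That is under 15% if the Negative Control Week 8 mean exceeds 0.234/0.15 = 1.56 (1.39 to 1.76 for SD 0.55 to 0.70). For the planning difference the limit is 0.33/0.15 = 2.2. This uses the change-score SD for raw scores, equal baselines and an unadjusted t-test, and the Week 8 mean is not given. It shows that two different criteria can differ. It says nothing about the table reference, the footnote or the sign.

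**The case for a change.** The best case for acting has four parts.

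- **The label concerns a competitor's product.** Four percentages would appear under a footnote that ties them to a Ministry of Health requirement stated elsewhere for the Negative Control. The mismatch stands. But the footnote makes no 15% claim, and SAP 4.8 presents the Positive Control figure as an addition.
- **Footnote [1] describes another quantity.** It concerns adjusted differences in change from baseline, and with baseline imbalance the raw percentage could have the opposite sign. That is true of the estimates. The meaning of a sign does not shift, because it depends on the scale and on the order of subtraction, and both are the same.
- **Section 5 omits the Positive Control percentage.** It does. However, Test versus Control Product 2 is already an exploratory comparison on both scales at both visits in Protocol 10.2.4. An untested percentage for the same pair, announced openly in SAP 4.8, is extra presentation and not a new analysis.
- **The role of the figure is not spelled out.** Protocol Section 2 asks that the Week 8 Schiff difference be clinically relevant as well as significant, and gives no threshold. Nothing links that clause to 15%. The percentage sits under other analyses in both documents, to be calculated and presented. Saying how the guideline itself reads the figure would need a source that is not part of these documents.

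**Conclusion.** No change to the plan follows. Two clerical slips stand: the table numbers in SAP 4.8 do not match the shell, and footnote [2] is looser than SAP 4.8 and Protocol 10.2.10 about the comparator. The missing sign is an omission that the scales and footnote [1] fill.

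The effect on results is nil. All eight percentages keep their values; the primary test, its estimate, the power and the success rule are untouched. The practical cost is a query at programming, settled by the only shell that shows the column. Anyone reissuing the SAP for another reason could tidy both places, but no conclusion depends on it.

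This rests on two assumptions: that the tactile tables follow the Schiff layout, as the programming note implies, and that the percentage stays descriptive, as its place in both documents indicates. The list of data displays is an attached worksheet that could not be read here.
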